12. STATISTICAL ANALYSIS

- Describe how your data will be used to test the hypotheses.
- State clearly what variables will be tested and what statistical tests will be used.
- *Include sample size calculations.*
- If this is a pilot study, state which variables will be examined for hypothesis generation in later studies.

A stepped-wedge cluster randomization (CR) design will be implemented. After a baseline period of six months, two clusters (grouped clinics) will be randomly assigned in month 7 and by month 18, all of NYS will be running the campaign. This strategy allows each region to serve as its own control³⁷. The treatment effect can be modeled as a random effect at the cluster level which will accommodate treatment heterogeneity across the clinics. We grouped the 21 OTNY sites into 6 clusters based on geolocation as well as the total number of FEP referrals at each clinic between 10/01/2017 to 09/30/2018. We combined some regions to ensure that each cluster will be able to successfully meet recruitment criteria. The six clusters are; 1) Bronx, 2) Manhattan, 3) Queens, 4) Brooklyn, 5) Hudson River/Central NY, 6) Staten

Version Date: 6.9.22 Page 12 of 31

Island/Long-Island/Western NY. There will be a total of four 6-month time periods, including the baseline period where all 6 clusters receive the control treatment. All analyses for Aim 1 (hypotheses A and B) will be conducted within the Generalized Linear Mixed Models (GLMM) framework with an identity link for continuous outcomes and logit link for binary outcomes. Analyses for Aim 2 will be done using asymptotic z-tests for proportions after accounting for the variance inflation factors (VIF). Aim 3 is exploratory, and hence only 95% confidence intervals, accounting for VIFs, will be calculated for the rates.

Aim 1: Evaluate the effectiveness of a search engine ad campaign on reducing DUP and raising rates of FEP referrals by directly comparing DUP and FEP referrals pre and post campaign activation. Hypothesis A: Patients admitted to OTNY via campaign channels will demonstrate a significantly shorter DUP than those admitted to OTNY through traditional outreach prior to campaign activation.

DUP will be defined as per Compton³⁶. DUP onset will be defined as the first full threshold delusion or hallucination, lasting throughout the day for several days or several times a week, not limited to a few brief moments. The endpoint will be defined as treatment with an antipsychotic (DUP 1). Given that our aim is to connect patients with specialty care, we will also define the DUP endpoint (DUP II) as enrollment in OTNY.

OTNY programs currently assess DUP at each site locally as part of the intake process. The mean DUP (n=1222) from symptom onset to OTNY enrollment is reported to be 7.6 months (median 5.5 months). For the duration of the award, all de-identified DUP data routinely uploaded to OTNY central (as part of standard quality improvement) will be provided to research staff for analyses. We will compare DUP from each site prior to activing the campaign, to DUP during the active phase of the campaign, arriving both through the campaign as well as through traditional channels.

Power Analysis: Sample size calculations were done using Hemming and Taljaard's second strategy³⁸ for stepped wedge CR design, where a fixed number of clusters (6) and number of steps (3) was specified based on feasibility, and the required number of participants per site per period was determined as the positive solution of a quadratic equation. In addition, intracluster correlation (ICC) for the sites was also required. Mean DUP reported from the RAISE-ETP study³ was 179 weeks (SD = 249), and the ICC used for the original power analysis for the RAISE study was 0.1. Prior marketing campaigns have reduced DUP substantially^{5,6}. Assuming a 50% reduction with our new intervention, the sample size required at 80% power and α = 0.05, is 32 participants per 6-month period per cluster, leading to (32 x 4 x 6=) 768 participants for Aim 1. Based on existing OTNY enrollment data, the Bronx will receive approximately 30 new intakes per 6-month period. In order to compensate, we will be collecting DUP data from 40 participants per 6months period in the Manhattan and Brooklyn clusters. Power analysis was done only for the primary outcome (hypothesis A).

Version Date: 6.9.22 Page 13 of 31

Hypothesis B: Activating the campaign will significantly increase the number of FEP referrals and patients admitted to OTNY as compared to number of FEP referrals and patients admitted pre-campaign. All OTNY referral data are thoroughly recorded as part of treatment as usual and stored in a centralized database within OTNY central. Extracted information includes the name and contact details of the individual making the inquiry, reason for the inquiry, presenting symptoms, duration of symptoms, age of the prospective patient, and outcome of the referral including OTNY intake/acceptance or screen out. For the duration of the award, all de-identified referral data routinely uploaded to OTNY central will be provided to research staff for analyses. We will extract OTNY referral data from each site prior to activing the campaign to serve as baseline, and will continue to extract all OTNY inquiry data during the active campaign. Additional referrals arriving through dedicated campaign channels (email, phone calls, text, live chat, and two way video) will be recorded centrally by research staff. All FEP referrals will be provided an appointment for an evaluation at the nearest OTNY program and admission to the program will be recorded. All ineligible referrals will be referred to appropriate local services. Based on existing OTNY inquiry data as well as the results of our prior pilot initiatives, we anticipate approximately doubling weekly inquiries as a result of the campaign, arriving through campaign related channels over the course of the trial (30 additional referrals). Of those, we anticipate that 20% will be appropriate for OTNY (6 participants weekly) and that 4 of those individuals will be successfully enrolled each week as a result of the campaign. We will compare baseline rates of inquiries, number of FEP referrals, and number of patients admitted to OTNY in NYS prior to campaign activation, to rate of inquiries, number of FEP referrals, and number of patients admitted to OTNY in NYS while the campaign is active both arriving through the campaign, and traditional referral channels.

Aim 2: Determine the efficacy of a campaign targeting caregivers in promoting treatment initiation by comparing rates of OTNY enrollment arriving through the caregiver campaign to rates of enrollment arriving through the patient campaign. Hypothesis: Engaging caregivers online will significantly increase the likelihood of promoting treatment initiation of individuals with FEP as compared to engaging prospective patients alone.

Throughout the campaign, one dedicated landing page for each unique target audience (prospective patients and caregivers), will be promoted online, presenting each audience with a unique and identifiable campaign phone line, email, text line, and live chat options. We will compare rates of inquiries, number of FEP referrals, and number of patients admitted to OTNY throughout NYS arriving through the caregiver campaign to rates of inquiries, number of FEP referrals, and number of patients admitted to OTNY arriving through the participant campaign. Both campaigns will run in parallel and

Version Date: 6.9.22 Page 14 of 31

each will target a dedicated audience based on demographics (age) and online search query. For example, "I am hearing voices" will generate the participant ad/campaign, while "my daughter is acting strange" will generate an entirely different set of ads geared towards caregivers. Power Analysis: Current OTNY referral data suggest that caregivers including parents are 5 times more likely to initiate a referral inquiry as compared to prospective participants themselves. We therefore anticipate that at least 2/3 (66.7%) of campaign referrals (approximately 20 weekly) will be generated by the parent campaign. Based on OTNY referral data, we anticipate that 20% will be appropriate and all will be enrolled into OTNY. Sample size necessary to detect a prevalence of 66.7% for the caregiver campaign compared to the null hypothesis of equal rates for the two campaigns is 68, which has to be multiplied by the design effect (variance inflation factor), [1 + (n-1)p], to get required sample size. As ICC (p) ranges from 0.01 to 0.06, the design effect will range from 1.67 to 5.02 and the sample size required will vary from 114 to 342. Although there are 24 six-month time periods from all clusters (4 per cluster and 6 clusters, $4 \times 6 = 24$) based on the stepped wedge design for Aim 1, only 12 of them will have the campaign. Based on recent OTNY referral data, the number of enrolled subjects per cluster in a 6-month period varied from 26 to 34, with an average of approximately 30. Thus, we expect to have (30 x 12) 360 subjects enrolled from the campaign part of the stepped wedge design. This sample size will be sufficient to detect the hypothesized difference in rates (66.7% vs. 33.3%) at 80% power and α = 0.05, with an ICC as high as 0.06.

Aim 3: Explore which methods of online engagement are most effective at promoting treatment initiation by comparing rates of OTNY enrollment of individuals interacting with research staff via live chat or two-way video to rates of enrollment of individuals utilizing text, email, and/or phone alone. Hypothesis: individuals with FEP who engage via two-way video or live chat will be significantly more likely to initiate in-person contact compared to individuals with FEP who engage via text, email, and/or phone alone.

The campaign will encourage all website visitors to interact with research staff via phone, email, text, live chat, or two way video. During these interactions, research staff will obtain information regarding the eligibility of each user and facilitate treatment initiation if indicated as would be done for any other traditional OTNY referral. Research staff will record as much data as the user is willing to provide at the time. This includes the name and contact details of the individual, presenting concerns, presenting symptoms, duration of symptoms, age of the prospective patient, and outcome of the discussion including OTNY intake or screen out. As early help seeking is likely an ongoing process for many, users will be offered the opportunity to repeatedly return to our landing page as many times as they wish for ongoing online support. Each interaction will be recorded. Individuals with FEP will be referred to a local OTNY program for assessment. Based on rates of live chat

Version Date: 6.9.22 Page 15 of 31

utilization in prior marketing initiatives³², we anticipate that at least 30% of campaign website visitors will engage live chat/two way video at least once. Based on OTNY referral data, we anticipate that 20% will be eligible for OTNY. We will compare the rates of treatment initiation of individuals with FEP who engage in online two-way video or live chat support to rates of treatment initiation of individuals with FEP who interact with the campaign through phone, email, or text alone. Analysis for Aim 3 will be exploratory in nature, and hence a power analysis was not done.

In order to analyze qualitative interviews conducted throughout the trial, the study team would like to send the interview data to a Northwell approved transcription service (Perry Johnson & Associates). We will try to obtain verbal consent from all participants prior to sharing their data. If any participant refuses to provide consent, their data will not be sent for transcription.

Version Date: 6.9.22 Page 16 of 31

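### The activation order is drawn without a stated restriction, so there is a 1-in-5 chance that the two clusters holding all areas outside New York City start together; a one-sentence restriction would halve the resulting sensitivity, not remove it

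*Combined protocol and SAP*

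**What the plan says.** All of this is in Section 12 (Statistical Analysis).

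- **Order of activation.** After the baseline, "two clusters (grouped clinics) will be randomly assigned in month 7". The section adds that the whole state is covered by month 18. It gives no stratification, balance rule or other limit on the order.
- **Layout.** "There will be a total of four 6-month time periods, including the baseline period where all 6 clusters receive the control treatment". The Aim 1 power paragraph describes a calculation "where a fixed number of clusters (6) and number of steps (3) was specified based on feasibility". The Aim 2 power paragraph counts 24 cluster-periods and says "only 12 of them will have the campaign".
- **Clusters.** "We grouped the 21 OTNY sites into 6 clusters based on geolocation as well as the total number of FEP referrals at each clinic". They are "1) Bronx, 2) Manhattan, 3) Queens, 4) Brooklyn, 5) Hudson River/Central NY, 6) Staten Island/Long-Island/Western NY". Geography therefore shaped the clusters but not their order.
- **Analysis.** Aim 1 uses a generalized linear mixed model, with an identity link for continuous outcomes. Each region is said to act as its own control. No period term and no region-by-period term is named.

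**The concern.** In a stepped-wedge trial the campaign effect is judged partly from clusters that are active while others still wait. With two clusters per step, one draw can make that comparison line up with geography. If clusters 5 and 6 both start last, every active cluster in period 3 is a city borough and the only two waiting clusters are the ones outside the city. If both start first, period 2 is the mirror image.

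Letting each region act as its own control removes stable differences between regions. It does not remove a change in duration of untreated psychosis (DUP) or in referrals that occurs in the city and not elsewhere, or the reverse. Period effects common to all clusters do not remove it either. Region-by-period terms would, but they cost more precision when the two clusters switch together. Once the order is drawn, the shared start cannot be undone.

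**Working it through.** **Inputs from Section 12.** Mean DUP 179 weeks, SD 249, ICC 0.1, a 50% reduction (89.5 weeks), 80% power, α = 0.05 (taken as two-sided), 6 clusters, 3 steps, 4 periods, 32 patients per cluster-period.

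**Assumptions.** Fixed period effects are added because the plan names none. Two clusters per step at steps 2 and 3 is inferred: 2 × (3 + 2 + 1) = 12 campaign cluster-periods, which matches the Aim 2 count. Six-month steps would start in months 7, 13 and 19, which does not fit full coverage by month 18; the plan should reconcile this.

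**1. The plan's own figure.** Unadjusted total = 2 × 2 × (1.96 + 0.8416)² × 249² / 89.5² = 243.0. The stepped-wedge design effect at n = 32 is

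[1 + 0.1(96 + 32 − 1)] / [1 + 0.1(48 + 32 − 1)] × 3(0.9) / [2(3 − 1/3)] = (13.7 / 8.9) × 0.50625 = 0.779.

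Solving n = 243.0 × DE(n) / 6 gives 31.5, rounded up to 32, and 32 × 24 = 768, as stated. Generalised least squares (GLS) with random cluster and fixed period effects gives SE 31.7 weeks and power 80.5%. This SE is the same for every order.

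**2. Chance of a shared step.** There are 6!/(2!2!2!) = 90 orders. Clusters 5 and 6 share a step in 3 × 4!/(2!2!) = 18 of them, or 20% (6 at each step). The all-city versus all-elsewhere period arises only when both are first or both last: 12 of 90, or 13%.

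**3. Bias from a lasting regional shift.** The GLS weights on clusters 5 and 6 give the bias as a fraction of a shift that begins in period 2, 3 or 4 and is not shared by the boroughs:

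| Steps of clusters 5 and 6 | From period 2 | From period 3 | From period 4 |
|---|---|---|---|
| both 1 | 0.35 | −0.15 | −0.27 |
| both 2 | 0 | 0.385 | 0 |
| both 3 | −0.35 | −0.23 | 0.27 |
| 1 and 2 | 0.17 | 0.12 | −0.13 |
| 1 and 3 | 0 | −0.19 | 0 |
| 2 and 3 | −0.17 | 0.08 | 0.13 |

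The worst case is 0.385 shared against 0.192 split. A shock confined to one period can reach 0.50 shared against 0.25 split. Fixed cluster effects give the same pattern for a lasting shift (0.40 against 0.20). The mean bias over all orders is zero, with or without a restriction. For a linear differential trend, the root-mean-square bias over the orders allowed falls from 0.182 (all 90) to 0.144 (the 72 split orders), which is 21%.

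**4. Type I error under random period shocks.** Suppose an independent city-versus-elsewhere shock of SD s in each period. It adds error of SD c × s, where c is the root sum of squares of the summed weights: 0.609 shared, 0.305 split. Type I error = 2[1 − Φ(1.96 × 31.7 / √(31.7² + (c·s)²))]. The free-draw column is 0.2 × shared + 0.8 × split; the restricted draw equals the split column.

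| Assumed s (weeks) | Shared | Split | Free draw |
|---|---|---|---|
| 10 | 5.4% | 5.1% | 5.2% |
| 17.5 | 6.3% | 5.3% | 5.5% |
| 25 | 7.7% | 5.7% | 6.1% |
| 35 | 10.4% | 6.3% | 7.1% |

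The value 35 is about √(0.2 × 0.1 × 249²) = 35.2, that is, 20% of the between-cluster variance. No value of s comes from the documents.

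**5. With region-by-period terms.** If the step is shared, the SE is 47.7 (both first or both last) or 40.5 (both middle), with a mean of 45.3 and power 47% to 60%, about 51% on average. If split, the SE is 33.4 to 34.2, with a mean of 33.9 and power 74% to 77%, about 75% on average. Over a free draw, average power is 0.2 × 51 + 0.8 × 75 = 70%.

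**The case against.** - **Small expected gain.** The decision is between a free and a restricted draw, not between a bad and a good order. On that contrast, type I error improves by 0.8 points at most in the range shown (7.1% to 6.3%), and bias is zero on average either way. This stands. The case for restricting is that the trial runs one order only and avoiding a poor one costs almost nothing.
- **Shock size unsupported.** Section 12 gives a mean DUP to OnTrackNY enrollment of 7.6 months, about 33 weeks (7.6 × 52/12), so a 35-week shock exceeds the whole local mean. This stands, and is why a range is shown. The bias fractions in step 3 do not depend on the outcome's scale.
- **The regional split is a judgement.** Cluster 6 includes Staten Island and joins Long Island to Western NY; site and patient shares are not given. No passage shows that the city and elsewhere changed differently, or that the areas outside the city move together. This stands. However, the plan itself grouped sites by geography, so using geography to constrain the order is reasonable.
- **Possibly too late.** The document is dated 6.9.22, and parts of Section 25 speak of participants' choices in the past tense, which suggests that campaign activity had begun. The documents do not say whether the order was drawn. If it was, only the reporting and the sensitivity analysis remain.
- **Silence is not proof.** An unstated restriction may be a reporting gap; the free draw is the plain reading.

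**Conclusion.** The point holds as a cheap design improvement. As written, the plan leaves a 20% chance that clusters 5 and 6 start together. That order doubles the sensitivity of the Aim 1 effect to a differential regional change (worst case about 0.39 against 0.19 of a lasting shift) and lowers power with region-by-period terms from about 75% to about 51%.

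A reader might infer three stronger things that the documents do not support:

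- **The campaign would be wholly confounded with city versus elsewhere.** It would not. Stable differences drop out, and the four borough clusters still contrast with one another.
- **Separating the two clusters removes the problem.** It halves the sensitivity; split orders keep a residual.
- **The trial's type I error is about 10%.** That figure needs both the one-in-five order and the largest assumed shock.

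The sizes rest on the plan's SD, ICC and cell size, on fixed period effects that it does not name, and on treating clusters 5 and 6 as one region.

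**What to change.** **If the order is not yet drawn**, add to Section 12: The order of activation is drawn at random from the 72 of 90 allocations in which Hudson River/Central NY and Staten Island/Long Island/Western NY start in different steps; any randomisation-based test uses the same 72.

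**In either case**, state which type of order occurred (shared or split, and at which steps), and pre-specify a sensitivity analysis for Aim 1 that adds region-by-period terms to a model with period effects. Give the patient shares within cluster 6 so that readers can judge the regional split.

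**Cost.** One or two sentences and an allocation list, with no added patients. Each cluster keeps a 1/3 chance of each step, and the main SE stays at 31.7 weeks. The downsides are 72 rather than 90 allocations for a randomisation test, a 25% rather than 20% chance that either of these clusters shares a step with any given borough, and lower precision in the sensitivity analysis (SE 33.9 on average if split, 45.3 if shared).

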the course of illness development, as well as individuals who might not otherwise come into contact with traditional referral sources. In response to this challenge, Northwell Health's early psychosis research team is collaborating with Strong365, a nonprofit initiative dedicated to raising early psychosis intervention awareness, to develop and test a proactive and targeted comprehensive digital media marketing campaign designed to facilitate help-seeking and encourage treatment initiation in prospective patients with FEP and their caregivers. Our team will take advantage of search engine advertising, which allows advertisers (researchers) to select keywords/phrases and create linked advertisements appearing as a strategically placed search result. Our dedicated ads will appear in response to online search queries conducted by prospective patients and their caregivers throughout New York State (NYS) that align with the campaign's pre-selected keywords/phrases. Individuals who click on the ads will be immediately directed to our campaign landing page/website, and offered a variety of established, innovative, and interactive online engagement tools intended to instantly connect users with coordinated specialty care (CSC) staff and to facilitate earlier treatment initiation.

Campaign referrals will be centralized and individuals with FEP will be enrolled into OnTrackNY (OTNY), a network of 21 dedicated early psychosis intervention programs throughout NYS. The campaign will target individuals as well as their friends, family, and caregivers, searching for information online. We will measure the DUP of individuals enrolled into OTNY before and after campaign activation and track the impact of the campaign on the number of FEP referrals and number of patients admitted to OTNY in NYS. Furthermore, we aim to identify the campaign target audience most effective at promoting treatment initiation as well as the online tools and resources most effective at encouraging treatment initiation of identified individuals with FEP. We will additionally explore the online trajectories to care of individuals with FEP engaging with the campaign.

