4. OBJECTIVE(S)/SPECIFIC AIMS AND HYPOTHESES

- A concise statement of the goal(s) of the current study.
- *The rationale for and specific objectives of the study.*
- The goals and the hypothesis to be tested should be stated.

Aim 1: Evaluate the effectiveness of a search engine ad campaign on reducing DUP and raising rates of FEP referrals by directly comparing DUP and FEP referrals pre-campaign to DUP and FEP referrals during the campaign. Hypothesis A: Patients admitted to OTNY via campaign channels will demonstrate significantly shorter DUP than those admitted to OTNY through traditional outreach prior to campaign activation. Hypothesis B: Activating the campaign will significantly increase the number of FEP referrals and patients admitted to OTNY as compared to the number of FEP referrals and patients to OTNY admitted pre-campaign activation.

Version Date: 6.9.22 Page 6 of 31

Aim 2: Determine the efficacy of a campaign targeting caregivers in promoting treatment initiation by comparing rates of OTNY enrollment arriving through the caregiver campaign to rates of enrollment arriving through the patient campaign. Hypothesis: Engaging caregivers online will significantly increase the likelihood of promoting treatment initiation for individuals with FEP as compared to engaging prospective patients online. Aim 3: Explore which methods of online engagement are most effective at promoting treatment initiation by comparing rates of OTNY enrollment of individuals with FEP interacting with research staff via two-way video and live chat to rates of enrollment of individuals with FEP utilizing text, email, and/or phone alone. Hypothesis: Individuals with FEP who engage via two-way video and live chat will be significantly more likely to initiate in-person contact compared to individuals with FEP who engage via text, email, and/or phone alone.

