6. RECRUITMENT METHODS

- *Describe the source of potential subjects*
- Describe the methods that will be used to identify potential subjects
- Describe any materials that will be used to recruit subjects. A copy of any advertisements (flyers, radio scripts, etc.) should be submitted along with the protocol.
- If monetary compensation is to be offered, this should be indicated in the protocol

Referrals for the study will come from self-response to the search engine ads. Those individual who interact with research staff via phone, text, email, live chat, or two way video will be greeted by a member of the study team who will inform users that as part of efforts to improve services, we'll be using some of the information provided to connect them to local care. If the individual does not want their information shared they can opt out. Patients who on initial evaluation are deemed not to be capable of giving verbal informed consent will not be evaluated further for the study. Patients who are deemed capable of giving verbal informed consent will then be provided with a full and complete description of the study.

Participants who are deemed most likely to be eligible for a referral to an early intervention clinic (based on their responses to the self-screener and/or live chat with research staff) and who choose not to progress along their pathway to care and/or accept a referral to care, will be re-approached by research staff (via the provided contact information) to participate in an additional optional 10 minute qualitative interview. Verbal consent for completion of this additional interview will be obtained. The goal of the interview will be to explore barriers in the online pathways to care and ultimately improve future iterations of the campaign. Questions will be open ended and explore personal motivations for deciding against pursuing formal care at this time.

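### The primary DUP hypothesis tests a self-selected group that the randomisation does not protect, conflicts with the before/during comparison stated elsewhere, and the sample size does not say who makes up the exposed group

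*Combined protocol and SAP*

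**What the plan says.** Section 12 states Hypothesis A as "Patients admitted to OTNY via campaign channels will demonstrate a significantly shorter DUP than those admitted to OTNY through traditional outreach prior to campaign activation", and section 4 gives it in almost the same words. The Aim 1 power paragraph in section 12 identifies it as primary: "Power analysis was done only for the primary outcome (hypothesis A".

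Three other places describe a different comparison:

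- Section 2 (Brief Summary): "We will measure the DUP of individuals enrolled into OTNY before and after campaign activation".
- Section 12, the Aim 1 sentence directly above Hypothesis A: "directly comparing DUP and FEP referrals pre and post campaign activation".
- Section 12, the paragraph on DUP data, which compares each site's DUP before activation "to DUP during the active phase of the campaign, arriving both through the campaign as well as through traditional channels". It does not say whether the two routes are pooled or each set against baseline.

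Section 6 says how people reach the campaign channel: "Referrals for the study will come from self-response to the search engine ads". Randomisation, in section 12, is of six clusters of clinics to campaign start times over four 6-month periods. The analysis is a GLMM with an identity link for continuous outcomes, and a cluster-level random treatment effect is mentioned as possible. The sample size takes a DUP mean of 179 weeks, SD 249 and ICC 0.1. "Assuming a 50% reduction with our new intervention", it arrives at 32 participants per cluster-period and 768 in total. Section 10 (Endpoints) is marked N/A, so it does not settle the contrast.

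**The concern.** In a stepped wedge the protected comparison is between cluster-periods with and without the campaign, because only the activation date is randomised. Hypothesis A keeps the control cluster-periods but replaces the exposed ones with the people in them who answered an ad. That membership is decided by the individual after activation. If ad-responders differ from other FEP patients in DUP for reasons unrelated to the campaign, the difference is estimated as a campaign effect, and adjusting for calendar period does not remove it.

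Two analysts working from this text could also run different primary tests: one restricted to campaign entrants, one on everyone admitted during the campaign. The two have different susceptibility to selection, different numbers per cell and, depending on who is assumed to benefit, very different power.

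**Working it through.** **Inputs from the plan.** Mean 179 weeks, SD 249, ICC 0.1, 50% reduction = 89.5 weeks, alpha 0.05 (taken as two-sided), 6 clusters, 4 periods, 3 steps (section 12). Existing enrolment is 8 a week and expected campaign enrolment 4 a week (sections 5 and 8). Two clusters are assumed to start at each of periods 2, 3 and 4, giving 12 exposed cells, the number the Aim 2 power paragraph uses.

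**Model.** Random cluster intercept, fixed period effects, treatment effect θ. With m patients in a cell, cluster i has covariance V_i = diag(SD²(1 − ICC)/m) + ICC·SD²·J, where J is the all-ones matrix. SE(θ) is the root of the θ element of (Σ D_i′V_i⁻¹D_i)⁻¹, where D_i is the design matrix. P(significant) = Φ(δ/SE − 1.96) + Φ(−δ/SE − 1.96).

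**Step 1: the plan's own figure.** Individually randomised n per arm = 2 × (1.960 + 0.842)² × 249² / 89.5² = 121.5. With the stepped-wedge design effect this becomes 31.55, so 32 per cell and 32 × 24 = 768. At 32 per cell SE = 31.73 and power = 80.5%. The figure reproduces. Without period effects, 11 per cell would be enough (81.5%), so the stated 32 already assumes them.

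**Step 2: patients per cell.**

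- Control cell: 8 × 26 / 6 = 34.7.
- Campaign entrants per exposed cell, spread evenly: 4 × 26 / 6 = 17.3, or 17.3 × 12 = 208 in all.
- All admissions per exposed cell: 34.7 + 17.3 = 52, of whom 4/12 = one third are campaign entrants.
- The Aim 2 paragraph instead expects 30 × 12 = 360 from the campaign part of the design. Its 30 is the recent average enrolment per cluster-period.

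**Step 3: selection alone, no campaign effect.** The selection sizes are assumptions. Under Hypothesis A the spurious difference is the full selection. In the all-admissions contrast it is one third of that.

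| DUP difference of ad-responders | Hypothesis A (32 control / 17.3 exposed, SE 36.96) | All admissions (32/32 to 34.7/52, SE 31.73 to 27.72) |
|---|---|---|
| 10% (17.9 weeks) | 7.7% | 5.4-5.5% |
| 20% (35.8 weeks) | 16.2% | 6.6-7.1% |
| 30% (53.7 weeks) | 30.6% | 8.7-9.9% |

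Worked example at 20%: 35.8 / 36.96 = 0.969; Φ(−0.991) + Φ(−2.929) = 0.162.

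**Step 4: power of Hypothesis A as worded (89.5 weeks).**

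- 32/17.3: SE 36.96, 67.8%. 34.7/17.3: SE 36.32, 69.3%.
- If the 360 are all campaign entrants (30 per exposed cell): 78.1% with 30 per control cell, 80.8% with 34.7.

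**Step 5: power for all admissions.**

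- If 50% is the average over everyone admitted in the active phase: 80.5% at 32/32 and 89.8% at 34.7/52.
- If only the campaign third gains 50%, the average is 89.5 / 3 = 29.8 weeks: 15.6% and 19.0%.
- The same case at OTNY's own mean of 7.6 months (3.8 / 3 = 1.27 months), with an assumed SD of 9 down to 6 months: about 20% (32/32, SD 9, SE 1.147) to 47% (34.7/52, SD 6, SE 0.668).
- Average reduction needed for 80% power (2.80 × SE): 88.9 weeks (49.7%) or 77.7 weeks (43.4%) at plan inputs. At OTNY inputs it is 3.21 months (42%) down to 1.87 months (25%).

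**The case against.** The best defence is that Hypothesis A is loosely worded beside a workable analysis. The Aim 1 sentence, the Brief Summary and the DUP data paragraph all describe before versus during within a stepped-wedge GLMM, and data on every admission will be available. That is fair as a reading of intent. It does not settle the matter, because the plan ties its primary outcome and its power to Hypothesis A by name.

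Four stronger readings are tempting, and the documents do not support them:

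- *That the plan names no primary contrast.* It does name one, Hypothesis A. The fault is that this contrast is unprotected and contradicted elsewhere.
- *That the model leaves out calendar time.* Section 12 gives a framework and link functions and is silent on fixed effects. It lays out four periods, and 32 per cell arises only with period effects. This is a term to be written down, not evidence that it was excluded.
- *That selection must flatter the campaign.* The sign is unknown. The Brief Summary expects to reach people outside the usual referral routes, and they could have longer DUP, which would bias the test against the campaign.
- *That 32 or 768 is miscalculated.* Both reproduce.

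It is also true that comparing all admissions does not abolish selection: the campaign is expected to add patients, so the case mix may change.

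**Conclusion.** The point stands. The primary hypothesis as worded gives up the protection of the randomised activation date and contradicts three other statements of the comparison. At plan inputs, selection of 10 to 30% with no campaign effect makes it significant 7.7 to 30.6% of the time, in favour of the campaign if ad-responders have shorter DUP and against it if longer. The all-admissions contrast gives 5.4 to 9.9% under the same selection.

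The stated 80% is sound arithmetic for a group the plan does not define. For Hypothesis A it becomes 68-69% at four campaign enrolments a week, or about 78-81% if all 360 are campaign entrants. For all admissions it holds only if 50% is the average over everyone admitted in the active phase. If the benefit is confined to the campaign third, power is 16-19% at plan inputs and about 20-47% at OTNY's mean.

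The selection sizes and the OTNY SD are assumptions, as is a common SD in both conditions. The one-third case further assumes no effect on traditional-channel patients. All figures use a normal reference with six clusters. A t reference would lower the 80.5% to about 75% on 14 df or 57% on 4 df. The unlisted period term is a clarification within this point, not a separate error.

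**What to change.** 1. Make the primary contrast the DUP of all OTNY admissions in campaign-on versus campaign-off cluster-periods, by randomised activation date, and reword Hypothesis A in sections 4 and 12 to match. State that the two arrival routes are pooled.
2. List the model terms: fixed effects for the four periods, as the sample size already assumes, a random cluster effect, and whether the random treatment effect is included.
3. Make campaign-channel versus traditional-channel a secondary comparison, labelled non-randomised.
4. Restate power for the named contrast, giving the assumed campaign share of exposed admissions and who receives the 50% reduction. Reconcile four campaign enrolments a week (about 208 over the 12 exposed cells) with the 360 in Aim 2.

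No new data are needed, since section 12 already has OTNY central supplying DUP data to the research staff. The cost is that the restated power may be less favourable: 80% needs an average reduction of 43-50% over all active-phase admissions at plan inputs, or about 25-42% at OTNY inputs. The plan should also state as a limitation that the all-admissions contrast still reflects any change in who is admitted.
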